9.1	Investigator Responsibilities	67
9.1.1	Good Clinical Practice.....	67
9.1.2	Financial Disclosure	68
9.1.3	Informed Consent Process.....	68

9.1.4	Source Documents.....	68
9.1.5	Data Protection.....	69
9.2	Sponsor Responsibilities.....	70
9.2.1	Emergency Medical Support.....	71
9.2.2	Clinical Study Insurance and Compensation to Subjects.....	71
9.2.3	Clinical Study Report.....	71
9.2.4	Publication.....	71
9.2.5	Dissemination of Clinical Study Data.....	72
9.2.6	Study and Site Closure.....	72
9.3	Regulatory and Ethical Considerations.....	73
9.4	Data Quality Assurance.....	73
10	References.....	75
11	Appendices.....	77
Appendix 1	Abbreviations.....	78
Appendix 2	Sample Quality of Life Questionnaire.....	82
Appendix 3	Guidance for 6-Minute Walk Test.....	83
Appendix 4	Borg Dyspnea Index.....	87
Appendix 5	Management of Abnormal and Medically Important Laboratory Abnormality.....	89
Appendix 6	Investigator Signature Page.....	90

List of Figures

Figure 1	Study Design of AV-101-003.....	8
----------	---------------------------------	---

List of Tables

Table 1	Schedule of Assessments.....	13
Table 2	Laboratory Assessment Parameters.....	39
Table 3	Variables Included in the REVEAL Lite 2 Risk Calculator.....	42
Table 4	Protocol Defined Highly Effective Forms of Contraception.....	56

Protocol Synopsis

Aerovate Therapeutics, Inc.
[name]
United States of America

Protocol Title: IMPAHCT-FUL: A Long-Term Extension, Multi-Center Safety Study of AV-101 in Subjects With Pulmonary Arterial Hypertension (PAH) Who Have Completed Study AV-101-002

Short Title: Inhaled Imatinib Pulmonary Arterial Hypertension Clinical Trial – Follow Up Long Term Extension (IMPAHCT-FUL).

Rationale:

Clinical efficacy of oral imatinib mesylate in the treatment of PAH was observed in Functional Class II-IV patients in the Phase 3 IMPRES trial, in which the primary endpoint, six minute walk distance (6MWD), as well as secondary endpoints measuring pulmonary vascular resistance (PVR), mean pulmonary arterial pressure (mPAP), cardiac output (CO), and N-Terminal Prohormone-B Natriuretic Peptide (NT-proBNP) all showed statistically significant and therapeutically relevant improvements on top of the maximal standard of care ([Hoeper et al., 2013](#)). However, oral imatinib was not well tolerated and further clinical development was halted.

Given the demonstrated clinical efficacy of oral imatinib in PAH, Aerovate is developing a dry powder inhaled imatinib, AV-101, to target the delivery of imatinib to the diseased organ, the lungs. Inhaled administration of AV-101 is expected to provide rapid local exposure of respiratory tissue to imatinib with a lower dose and lower systemic exposure compared to Gleevec® oral tablets. Aerovate expects that inhaled AV-101 administration will result in a more favorable benefit/risk profile than that observed with oral Gleevec administration. Therefore, subjects who successfully complete the 24-week placebo-controlled trial (AV-101-002) will be offered the opportunity to continue into this long-term extension (LTE) study.

Overview and Objectives:

The primary objective of the study is to establish the long-term safety of AV-101. The long-term effects of AV-101 on efficacy measures (e.g., 6MWD, NT-proBNP, cardiac echo) will also be assessed.

Overall Design:

Study AV-101-003 is a long-term extension (LTE) follow up study where recruitment of subjects will continue as the parent study (AV-101-002) progresses from Phase 2b to Phase 3. Subjects who were on placebo in Phase 2b and the Intermediate Part of the study who enroll in the LTE study will be re-randomized to one of the 3 active AV-101 doses until such time as the optimal dose has been selected. Once the optimal dose of AV-101 has been selected, all subjects will be transitioned

to the optimal dose while they continue in the LTE, and subjects completing the Intermediate Part or parent study Phase 3 will enroll into the LTE study at the optimal dose.

Subjects enrolling into the LTE study will be closely followed for the first 24 weeks given that those who transition from placebo will be receiving AV-101 for the first time (See Schedule of Assessments [Table 1](#)). Study visits will be every 3 months after completing the first 24-week period. Investigators and subjects will remain blinded to the randomization in the parent study until the optimal dose has been selected for the Phase 3 part in AV-101-002.

Number of Study Sites: Approximately 140 sites globally

[figure not shown]
Number of Subjects: Up to approximately 462 subjects

Involvement of Special Committee(s): There will be an independent data safety monitoring board (DSMB) to oversee the safety and welfare of study subjects ([Section 3.3](#)).

[figure not shown]
Figure 1 Study Design of AV-101-003

Figure 1 presents the design schematic of this study.

For Subjects Entering the LTE from the Phase 2b and Intermediate Parts of AV-101-002

For Subjects Entering the LTE from the Phase 3 Part of AV-101-002

- A. Screening/Baseline Visit and procedures for the LTE will be conducted at the Week 24 Visit for AV-101-002.
- B. Once the optimal dose is selected for the parent Phase 3 Part of AV-101-002, subjects who enter the LTE from the Phase 2b Part and the Intermediate Part of AV-101-002 will be transitioned to the optimal dose.
- C. Once the AV-101 optimal dose has been selected, the LTE will no longer be blinded. Subjects enrolled during the Intermediate Part of AV-101-002 that enter the LTE study after the optimal dose is selected will be assigned to that dose upon completion of the Week 24 Visit for AV-101-002.

Target Population: Patients with Group 1 PAH who have successfully completed study AV-101-002.

Duration of Study Drug Treatment: The LTE study will continue until 31 December 2025 or until the Sponsor stops the study.

Diagnosis and Main Eligibility Criteria: For a complete list of study inclusion and exclusion criteria, please refer to [Section 4.1](#) and [4.2](#).

Key Inclusion Criteria:

To be eligible, a participant is required to be or have:

- Consented to participate in the LTE and has successfully completed the placebo-controlled 24-week Study AV-101-002.
- Female subjects of childbearing potential who have agreed to continue to use a highly effective form of contraception during the LTE and for at least 30 days after completing or discontinuing study treatment (highly effective forms of contraception are described in [Section 7.8](#)).

Key Exclusion Criteria:

Subjects meeting any of the following criteria:

- The Investigator believes that it would not be in the best interest of the subject to be included in the LTE e.g., for clinical or social reasons.
- Subjects who were not compliant with study medication in AV-101-002 as assessed by the Investigator.
- Applicable for France only: Persons referred to in Article L1122-2 of the French Public Health Code:
 - Person deprived of liberty by a judicial or administrative decision
 - Person under psychiatric care
 - Person admitted to a health or social institution for purposes other than research
 - Person who is the subject of a legal protection measure (tutelage, guardianship, safeguard of justice)
 - Person unable to express consent and who is not subject to a legal protection measure

Study Procedures/Frequency:

Subjects will be followed by the Investigator according to clinical practice, with formal (per protocol) assessments conducted at the Screening/Baseline and at other protocol Clinic Visits. Study visits will occur at Screening/Baseline, Weeks 1, 4, 8, 12, 16 and 24. After the Week 24 visit subjects will return to the clinic every 12 weeks for study assessments. There will be a 4-week follow up by telephone after the subject's End of Treatment (EOT) Visit.

If a subject withdraws consent, they should return for an ED Visit within 14 days following the last dose and they should have a Safety Follow-Up (FU) Visit 4 weeks after the ED Visit. Subjects will then be contacted for Vital Status every 24 weeks after the Safety Follow Up Visit by telephone until study completion.

Assessments that will be done at each visit can be found in the Schedule of Assessments ([Table 1](#)).

Test Product, Dose, and Mode of Administration:

Capsules of AV-101 inserted into a dry powder inhaler device for administration to subjects' lungs by inhalation.

Subjects entering the LTE study from the Phase 2b and Intermediate Parts of AV-101-002:
Capsule strength: 5 mg, 17.5 mg, or 35 mg AV-101. Administered Doses (2 capsules): 10 mg, 35 mg, or 70 mg AV-101, BID.

Subjects entering the LTE study from the Phase 3 Part of AV-101-002: AV-101 optimal dose, BID

If a subject down titrated the dose of AV-101 in Study AV-101-002 and successfully completed 24 weeks of treatment, the subject should begin the LTE study with 2 capsules BID. If the subject did not tolerate the 2 capsules, they may down titrate to one capsule in the LTE. At the time of the optimal dose selection and transition to the optimal dose in subjects who have down titrated in the LTE, the Investigator should decide whether it is clinically appropriate to transition these subjects given the tolerability history and optimal dose selection (Investigators will be unblinded to the treatment dose at this time). Down titration after subjects have switched to the optimal dose will be permitted.

Statistical Methods:

Summary analyses for this study will be performed periodically to generate safety and effectiveness data for regulatory submissions and for review by the Data Safety Monitoring Board (DSMB). Efficacy measures reported in the parent AV-101-002 study will also be collected in the LTE but only for subjects being treated with the open-label optimal AV-101 dose once it is identified. These efficacy measures will be labeled effectiveness measures for LTE reporting.

Safety and effectiveness data will be summarized by AV-101 treatment groups and all subjects combined at cumulative 24-week intervals. Levels in longitudinal continuous, categorical, and time-to-events data will be presented by time-intervals. LTE intervals will be divided into before and after optimal dose treatment. Continuous data will be summarized using the following descriptive statistics: number of observations, mean, standard deviation, standard error, median, minimum, and maximum. Categorical data will be summarized using frequencies and percentages. Changes from baseline will be calculated as the later value minus the baseline value. Baseline will be defined for all endpoints as the time of starting treatment with AV-101 in the parent study (AV-101-002) or baseline LTE. Baseline for subjects previously randomized to placebo will have their baseline defined at Week 24 of the parent study.

Trends or patterns over time in safety and effectiveness measures will be presented graphically, and in repeated measures models applicable to categorical or continuous data. Time-to-event analysis will be performed using Kaplan-Meier procedures as well as a time-to-event model with time-independent and time-varying covariates.

Study Endpoints

- Safety and tolerability of AV-101
- Survival
- Change from baseline in the 6MWD
- Change from baseline in NT-proBNP
- Time to Clinical Worsening events
- Achievement of the multi-component improvement parameters
 - Percent of subjects who achieve the multi-component parameters by visit
 - Time to achieving the multi-component improvement parameters
- Change in WHO Functional Class status
- Change from baseline in REVEAL Lite 2.0 risk score
- Change from baseline in QoL (emPHasis-10) Questionnaire score
- Change from baseline in Transthoracic Echo parameters of right ventricular (RV) function
- Change from baseline in hemodynamics (in subjects who have RHC measures)

Clinical Worsening Events will be defined as:

- Death (all causes)
- Hospitalization for worsening PAH
- Initiation of parenteral prostanoids
- $\geq 15\%$ decline from baseline in 6MWD accompanied with continued or worsening WHO FC III or IV symptoms. The decline in 6MWD must be confirmed with a repeat test on a different day within 2 weeks. (Baseline is defined by the randomization visit in Study AV-101-002 for those on AV-101 and the Week 24 visit for those on placebo in Study AV-101-002).

Clinical Improvement from baseline will be assessed by the proportion of subjects achieving all 3 of the following components at 6 month intervals:

- WHO FC improvement or maintenance of WHO FC II status
- NT-proBNP $\geq 30\%$ improvement or < 300 pg/ml
- 6MWD ≥ 30 -meter improvement

The change from baseline in the REVEAL Lite 2.0 risk score ([Benza, 2020](#)) at 6 month intervals classified as low, intermediate, or high risk will be assessed using the following variables to derive the risk score:

- Estimated Glomerular Filtration Rate (eGFR) in ml/min/1.73 m² or renal insufficiency if GFR is unavailable
- WHO FC

- Systolic blood pressure and heart rate
- 6MWD
- NT-proBNP

Transthoracic Echocardiogram will be assessed and evaluated at 6 month intervals.

Safety and tolerability of AV-101 will be assessed using the following:

- Adverse Events
- Pulmonary Function Tests at 24-week intervals (Spirometry including FEV₁ and FVC, peripheral oxygen saturations and DLCO [Diffusing Capacity of the Lungs for Carbon Monoxide])
- Safety Laboratory Tests at Weeks 4 and 12, and at 12-week intervals thereafter (including chemistry and complete blood count)

Adverse events will be collected throughout the study period.

Safety data analyses

The independent DSMB will monitor safety at regular intervals throughout the Phase 2b/3 study as well as during the LTE study. Details regarding the members, meeting frequency and stopping rules will be specified in the DSMB charter.

Blinding and unblinding considerations

The study will remain blinded until the optimal dose from Study AV-101-002 has been identified. In the event of a medical emergency, the Investigator will be able to receive the treatment assignment, if required to provide optimal care of the subject. Instructions for Emergency Unblinding can be found in the IWRS Manual. See also [Section 7.6](#) Procedures for Breaking the Treatment Code.

Compliance

The study will be conducted within the guidelines of the International Council for Harmonisation (ICH) Good Clinical Practice (GCP) as well as appropriate regulatory requirement(s).

Table 1 Schedule of Assessments

Study Procedure*	Screening / Baseline ¹	Week 1	Week 4	Week 8	Week 12	Week 16	Week 20†	Week 24	Every 12 Week Visits	Early Discontinuation or End of Treatment ²	Safety Follow Up ³	Vital Status Follow Up ¹⁰
Study Day	1	7 ± 1	29 ± 2	57 ± 2	85 ± 2	113 ± 2	141 ± 2	169 ± 2	Every 85 ± 2 thereafter		+30d ± 2	Every 169 ± 2
Visit Type	Clinic	Phone	Clinic	Phone	Clinic	Phone	Phone	Clinic	Clinic	Clinic	Phone	Phone
Written Informed Consent	X											
Medical History	X											
Physical Examination ⁴	X		X		X			X	X	X		
Vitals & Weight ⁵	X		X		X			X	X	X		
Chemistry & Hematology	X		X		X			X	X	X		
NT-proBNP	X		X		X			X	X	X		
Pregnancy Test ⁶	X		X	X	X	X	X	X	X	X		
12-Lead ECG	X		X					X		X		
Resting Transthoracic Echocardiography	X							X	X ⁷	X		
Quality of Life Questionnaire	X				X			X	X	X		
6MWT	X		X		X			X	X	X		
Borg Dyspnea Index	X		X		X			X	X	X		
Randomization ⁸	X											
Drug Dispensing	X		X		X			X	X			
IMP return/ Compliance			X		X			X	X	X		
WHO Functional Class	X		X		X			X	X	X		
Spirometry Test and Oxygen Saturation ⁹	X		X		X			X	X ⁷	X		
DLCO	X							X	X ⁷	X		

Study Procedure*	Screening / Baseline ¹	Week 1	Week 4	Week 8	Week 12	Week 16	Week 20†	Week 24	Every 12 Week Visits	Early Discontinuation or End of Treatment ²	Safety Follow Up ³	Vital Status Follow Up ¹⁰
Study Day	1	7 ± 1	29 ± 2	57 ± 2	85 ± 2	113 ± 2	141 ± 2	169 ± 2	Every 85 ± 2 thereafter		+30d ± 2	Every 169 ± 2
Visit Type	Clinic	Phone	Clinic	Phone	Clinic	Phone	Phone	Clinic	Clinic	Clinic	Phone	Phone
REVEAL Lite 2 Risk Score	X				X			X	X	X		
Concomitant Medications	X	X	X	X	X	X		X	X	X	X	
Clinical Worsening		X	X	X	X	X		X	X	X	X	
Adverse Events	X	X	X	X	X	X	X	X	X	X	X	
Vital Status		X	X	X	X	X		X	X	X	X	X

* *Unscheduled visits may occur at any time during the study with the assessments to be performed according to the Investigator's judgment. Unscheduled visits may also be necessary for study drug dispensing following temporary withdrawal as described in Sections 6.7 and 7.7.*

† *Week 20 phone visit is only for females of childbearing potential as the main purpose is to provide a reminder to perform home pregnancy testing.*

1. Screening assessments may be performed at the AV-101-002 Week 24 Visit. Study treatment re-randomization shall occur after all AV-101-002 Week 24 procedures are completed for subjects previously randomized to placebo, if LTE participation starts prior to identifying the optimal dose. All LTE participants will be treated with the optimal dose once that dose is identified, unless participants have been down titrated.
2. Subjects discontinuing study treatment must return to the site within 14 days for safety assessments; if this assessment does not correspond with a scheduled study visit, then an Early Discontinuation (ED) Visit will be performed. If the subject is unwilling or unable to come into the clinic for the ED or the End of Treatment Visit, then this visit with as many assessments as possible can be conducted by telephone.
3. The Safety Follow-Up Visit will be performed 30 days (± 2 days) after the ED Visit.
4. A focused physical examination (PE) will be performed at Baseline and clinic post-baseline visits.
5. Height will be recorded at the Screening Visit using the measurement taken from AV-101-002.
6. Urine pregnancy test for females of childbearing potential only. Additionally, home urine pregnancy testing is required every 4 weeks between study visits. When home pregnancy testing is required, a telephone call to the subject is required to confirm the test date, result of the test, lot number, and expiration date of the test (see Section 7.8). NOTE: Follicle Stimulating Hormone (FSH) test may be performed at Screening, per Investigator's discretion to confirm post-menopausal state. A reminder to perform home pregnancy testing is given during phone visits at Weeks 8, 16 and 20.
7. Resting Transthoracic Echocardiography, PFT's and DLCO to be performed every 24 weeks following Week 24 Visit.
8. Randomization or study drug allocation will be performed by IWRS.
9. Testing includes FEV₁, FVC, and peripheral oxygen saturations.
10. Vital Status will be collected every 24 weeks after the Safety Follow Up Visit by telephone until study completion.

1 Introduction

Aerovate Therapeutics Inc. (Aerovate) is developing AV-101 (imatinib powder for inhalation) for the treatment of pulmonary arterial hypertension (PAH; WHO Group 1) in adults with WHO Functional Class II–IV symptoms as a disease modifying drug to improve exercise capacity and delay disease progression. AV-101 is a drug-device combination product designed to deliver imatinib directly to respiratory tissues.

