6.2.1 Telephone Visits

Telephone Contacts are required at Week 1, Week 8, Week 16 and Safety FU. AE, Concomitant Medications, Clinical Worsening and Vital Status (when required) must be assessed. For women of childbearing potential, a reminder to perform home pregnancy testing is also provided during the telephone visits including an additional call at Week 20. In addition, Investigators are required to evaluate subjects for the presence of any signs or symptoms suggestive of intracranial bleeding such as: headache, confusion, vomiting, slurred speech, etc.

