6.2.4 Safety Follow Up Period

After the last dose of the IMP, subjects will be required to enter a 30-day Safety Follow Up Period.

Subjects who complete an ED Visit are also required to complete the 30-day Safety Follow Up Period.

Subjects will be contacted 30 days (± 2 days) after the ED Visit to review adverse events and concomitant medications. Ongoing AEs will be followed as outlined in Section 7.4. Subjects will then be contacted for Vital Status every 24 weeks after the Safety Follow Up Visit by telephone until study completion.

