6.8 Discontinuation of Study Drug and Subject Discontinuation/Withdrawal

6.8.1 Discontinuation of Study Drug

At the time of early study drug discontinuation subjects may elect to (1) discontinue from the study and agree to telephone contacts per the visit schedule, or (2) discontinue from the study, and withdraw consent to be contacted in the future for further collection of study-related data.

For subjects who withdraw from or are withdrawn from taking the study drug, every attempt should be made to follow the subject for long term outcomes. However, if a subject withdraws consent to be contacted, they must complete the Early Discontinuation (ED) Visit within 14 days of AV-101 discontinuation, and then the Safety Follow-Up visits as described in [Section 6.2.2](#) and [6.2.4](#).

For subjects who are lost to follow-up, or who died, Safety Follow-up Visits may not be possible. In any case, the appropriate eCRF section must be completed.

The subject must be discontinued from taking study drug in the event of any of the following:

Examples:

- Enrollment despite violation of an inclusion or exclusion criterion which, in the Investigator’s and/or Sponsor’s opinion, makes discontinuation of the subject necessary.
- Occurrence of an AE/SAE that makes discontinuation of study drug desired or considered necessary by the Investigator and/or the subject.
- Participation in any other interventional study during the duration of this study for which the Investigator considers discontinuation of the AV-101 necessary.
- Occurrence of pregnancy (for further details in case of pregnancy, refer to [Section 7.8](#)).
- If disease activity is considered unacceptably high and treatment escalation beyond permitted medication changes ([Section 5.9.1](#)) is warranted in the view of the Investigator.

- Anaphylaxis, anaphylactoid, or other severe or life-threatening hypersensitivity reactions, based on the Investigator judgement.
- Use of a nonpermitted medicine, as defined in [Section 5.9.2](#). This should first be confirmed with the CRO Medical Monitor before discontinuation of the study drug.
- Noncompliance, judged as significant by the Investigator or Sponsor including noncompliance to the required study considerations, as defined in [Section 5.8](#).
- Surgery considered by the Investigator or Sponsor to be major (see [Section 4.2](#)).

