Visits within a subject form a cluster. Estimated proportions by treatment group and visit will be reported. For Week 24 after optimal dose treatment, the log of odds and proportions of subjects who maintain or improve WHO FC and their 95%CI will be reported by treatment groups. Odd ratios (OR) and 95%CI for subjects always on optimal dose (Group 1) relative to those subjects on always on placebo (Group 4) will be reported. OR and 95%CI among subjects always on optimal dose (Group 1) relative to those of subjects on placebo and then active treatment (Group 3) and OR and 95%CI among subjects always on optimal dose (Group 1) relative to those of subjects on non-optimal dose (Group 2) will also be reported.

4) Time to Clinical Worsening

Time to clinical worsening while in the parent trial and LTE will be based on the first occurrence of any of the following events for each subject.

- Death
- Initiation of parenteral prostanoids
- Hospitalization for worsening PAH
- $\geq 15\%$ decline from baseline in 6MWD and accompanied with progression to or continued WHO FC III or IV symptoms

A subject is evaluated for experiencing any of the above components of clinical worsening throughout the parent trial and LTE study period. Time to clinical worsening is the number of days between the earliest occurrence of the clinical worsening component and the date of the first dose in the parent trial. With treatment groups that change over time intervals, event and censoring will be defined within each time interval. A subject who does not experience any of the clinical worsening component throughout a treatment period/interval is censored and is assigned time to worsening status by the end of the interval. Subjects who are lost to follow-up are typically considered censored. Supplemental analyses will be performed where subjects with an unknown clinical worsening event will be considered to

experience the event and the time to clinical worsening status is the last contact with the subject.

The probability of clinical worsening every 24 weeks after the first dose in the parent trial throughout the LTE will be reported, descriptively as well as based on a Cox model for time to clinical worsening while holding covariates at their means.

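### After Safety Follow Up only vital status is collected, so non-fatal clinical worsening in subjects who have stopped study drug is not ascertained, and Section 8.5.2 gives no censoring date for them

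*Combined protocol and SAP*

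**What the plan says.** Time to clinical worsening is a first-tier endpoint in Section 8.5.2 (item 4). Its components are death, start of parenteral prostanoids, hospitalisation for worsening PAH, and a 6MWD decline of at least 15% with WHO FC III or IV symptoms. On the observation period the section says: "A subject is evaluated for experiencing any of the above components of clinical worsening throughout the parent trial and LTE study period". Cox hazard ratios then compare Group 1 with Groups 4, 3 and 2.

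For subjects who stop study drug, Section 6.8.1 says that "every attempt should be made to follow the subject for long term outcomes", without naming any data item. The collection that is scheduled is this:

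- An early discontinuation (ED) visit: "Subjects discontinuing study treatment must return to the site within 14 days for safety assessments" (Table 1, footnote 2).
- A safety call: "Subjects will be contacted 30 days (± 2 days) after the ED Visit to review adverse events and concomitant medications" (Section 6.2.4). Table 1 also ticks Clinical Worsening here.
- After that: "Vital Status will be collected every 24 weeks after the Safety Follow Up Visit by telephone until study completion" (Table 1, footnote 10; Section 6.2.4 gives the same rule).

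In Table 1 the column "Vital Status Follow Up" carries a tick for vital status and nothing else. Section 6.2.1, which says what the telephone visits must assess, including worsening, lists these: "Telephone Contacts are required at Week 1, Week 8, Week 16 and Safety FU". The 24-weekly calls are not among them.

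**The concern.** The endpoint is defined over a longer period than the data collection supports. Once the safety call has passed, a hospitalisation for PAH or a start of parenteral prostanoids in a discontinued subject has no scheduled route into the database, although both could be asked on a call that is already planned. From then on the composite is, in effect, death alone.

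What this does to the estimate depends on how the subject is handled, and Section 8.5.2 does not say. It covers the end of a treatment interval and loss to follow-up, but a discontinuer who answers the telephone every 24 weeks is not obviously lost to follow-up. If that subject is censored at the safety call, the estimate is sound only if risk after stopping is like risk on drug. If the subject stays at risk, non-fatal events are missed whatever the risk. At stake are the reported worsening probabilities and what the hazard ratios mean.

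**Working it through.** **When enquiry ends.** The ED visit falls 0 to 14 days after last dose and the safety call 30 ± 2 days later. Earliest: 0 + 30 − 2 = 28 days. Latest: 14 + 30 + 2 = 46 days.

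**Is there another route?** Section 7.2 ends adverse event reporting at the last safety follow-up. After that, investigators need not look for serious events and report only those considered relevant to study drug. A PAH hospitalisation judged unrelated would not be picked up.

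**Size.** The documents give no event rate, discontinuation rate or event count for worsening, so there is no figure to reproduce. Everything below is an assumption used for illustration: worsening hazard on drug L = 0.25/year; discontinuation hazard d = 0.20/year; hazard after stopping rL with r = 1, 2 or 3; horizon T = 2 years; enquiry ends w = 30 days = 0.082 year after stopping.

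*True two-year worsening* is 1 − S, where S = e^(−(L+d)T) + d[e^(−rLT) − e^(−(L+d)T)]/(L + d − rL).

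- r = 1: S = e^(−0.5) = 0.607, so 39.3%.
- r = 2: S = 0.407 + 0.20(0.368 − 0.407)/(0.45 − 0.50) = 0.561, so 43.9%.
- r = 3: S = 0.407 + 0.20(0.223 − 0.407)/(0.45 − 0.75) = 0.529, so 47.1%.

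*(a) Censored at w.* Subjects still under enquiry but off drug number about dw = 0.0164 per subject on drug. The observed hazard is about L(1 + 0.0164r)/(1.0164): 0.250, 0.254 and 0.258 for r = 1, 2, 3. Kaplan-Meier gives 1 − e^(−2 × hazard), that is 39.3%, 39.8% and 40.3%.

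*Events lost.* With T′ = T − w = 1.918, first events later than w after stopping amount to e^(−rLw) × d × {(1 − e^(−(L+d)T′))/(L+d) − [e^(−rLT′) − e^(−(L+d)T′)]/(L + d − rL)}, which is 0.058, 0.098 and 0.126.

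*(b) Kept at risk, only deaths seen.* If 30% of events are fatal, the result is the true value minus 0.7 times the events lost: 0.393 − 0.7 × 0.058 = 0.352; 0.439 − 0.7 × 0.098 = 0.370; 0.471 − 0.7 × 0.126 = 0.383.

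| Risk off drug | True | (a) Censored at 30 days | Share of events lost | (b) Only deaths seen |
|---|---|---|---|---|
| unchanged | 39% | 39% | 15% | 35% |
| doubled | 44% | 40% | 22% | 37% |
| tripled | 47% | 40% | 27% | 38% |

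Column (b) ignores deaths that follow an unseen non-fatal event. Counting those as late events (hazard 0.3rL after day 30 for every discontinuer) gives 35%, 38% and 40%, which is still below the truth in each row.

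**Other assumed rates.** With L and d each between 0.10 and 0.20/year and enquiry ending at 44 days, censoring is unbiased at r = 1, too low by 1.3 to 3.5 points at r = 2, and by 2.3 to 6.1 points at r = 3. Keeping discontinuers at risk (20% to 40% of events fatal) is too low by 0.8 to 3.8 points at r = 1 and by up to 8.0 points at r = 3.

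**The case against.** Five things can be said for the plan.

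- **Much worsening is already captured.** The endpoint is time to first event. Worsening is ticked at every post-baseline contact up to the safety call, except the Week 20 pregnancy-test reminder. An event that prompts stopping is therefore normally recorded. This stands; the gap concerns subjects who stop without an earlier event.
- **A supplemental analysis exists.** Section 8.5.2 will count subjects with unknown worsening status as events at last contact. It is a useful extreme bound, but it recovers no event and no date, and it is unclear whether someone reached for vital status counts as unknown or which contact date would apply.
- **The analysis may be meant as on-treatment.** Events and censoring are defined within treatment intervals, with time-varying dose groups. That reading is possible, but it sits badly with evaluation throughout the study period and with Section 6.8.1, and no estimand or censoring date for discontinuers settles it.
- **This is a safety extension with no power claim for worsening.** True, and it limits the weight of the point.
- **The group comparison may barely move.** A reader might infer that the hazard ratios are biased. An example can be built: with discontinuation of 30% against 15%/year and tripled off-drug risk, a true ratio of 1.15 is observed as about 1.04. Neither input is in the documents. With an assumed 370/4, or about 90, per group and 40% having events (36 each), the standard error of the log ratio is √(1/36 + 1/36) = 0.24, against a shift of ln(1.15/1.04) = 0.10.

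A reader might also infer that the censoring is known to be informative. Section 6.8.1 does tie stopping to high disease activity and to adverse events, which makes it plausible, but no document gives risk after stopping, and at unchanged risk censoring at the safety call causes no bias. Nor is the 15-27% of events lost a measure of bias: 15% are lost in the unbiased case.

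**Conclusion.** The point holds as incomplete ascertainment together with an unstated censoring rule. Non-fatal worsening has no scheduled collection beyond about 28 to 46 days after last dose, although the analysis covers the full study period. This follows from Table 1 and Sections 6.2.1, 6.2.4, 7.2 and 8.5.2 and rests on no assumption.

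The size does rest on assumption. At 0.25/year worsening and 0.20/year discontinuation, the two-year figure is between 0 and about 7 points too low if discontinuers are censored soon after stopping. It is about 4 to 9 points too low if they stay at risk with only deaths seen, where the error is present even at unchanged off-drug risk. Informative censoring and a distorted between-group hazard ratio are possible consequences, not established ones. The change is worth making because the call already takes place and the endpoint is first-tier.

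**What to change.** 1. Add two dated questions to the existing 24-weekly call: hospitalisation for worsening PAH, and start of parenteral prostanoids. Tick Clinical Worsening in that column of Table 1, marked as limited to these two components, and amend footnote 10 and Sections 6.2.1 and 6.2.4 to match. This also gives the long-term outcomes in Section 6.8.1 a concrete content.
2. Use the answers in the time-to-worsening analysis.
3. State in Section 8.5.2 that discontinuers are censored for the composite at the last contact at which worsening was asked, and say whether the unknown-as-event analysis applies to subjects reached for vital status only.
4. Keep an analysis censored at Safety Follow Up as supportive.

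The cost is two questions, an eCRF field and consent wording. The limits are real: answers rest on recall over 24 weeks, subjects who refuse further contact cannot be asked, and the 6MWD component remains unobserved after stopping, so the composite is still not fully the same before and after discontinuation.
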